Diabetic foot ulceration (DFU) is a common and largely preventable complication. [1] While most of these ulcers can be treated successfully, some will persist and become infected. Ultimately, nearly one fifth of patients with infected lower-extremity diabetic ulcers will require amputation of the affected limb, resulting in staggering costs for both the patient and the healthcare system. Prevention by identifying people at higher risk is the key for better clinical management of such patients. It is not uncommon for patients suffering from diabetes to have concomitant lower extremity edema or even venous insufficiency[2-4] and they subsequently may benefit from graduated compression[5-7]. However, because of the common association of peripheral arterial disease (PAD) in patients with diabetes[8-10], most clinicians are reluctant to apply compressive dressings in fear of exacerbating the symptoms of PAD and the possible resulting gangrene[11].

Unfortunately, this area has received comparatively little attention from industry, academia, or insurance providers. A novel micro-mobile intermittent pneumatic foot compression device (AVEX Footbeat, Inc.) offers alternative means providing lower extremity compression. This device is portable and can be used in ambulatory settings providing increased venous blood and relief from concomitant lower extremity edema.

Section D: Purpose and Objectives

The purpose of this study is to conduct an observational study with N=30 patients to assess whether this micro-mobile foot compression device can help reduce lower extremity in patients with both diabetes and lower extremity edema without compromising the vascular supply.

The main purpose of this study is to determine if the device lessens edema. This study will also evaluate a new research device to see if it may help prevent diabetic foot ulcers. Additionally, it may potentially help delay progression of foot disease and produce a better quality of life by providing a better blood flow to foot and ankle.

Primary Endpoints: Reduction in lower extremity edema at 4 weeks of continuous device usage. Peripheral edema will be measured at baseline, 48 hours, 1 week and 4 weeks. Peripheral edema will be directly measured by traditional volume change assessment and indirectly by skin perfusion pressure assessment.

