Will pregnant women and/or fetuses (as described in 45 CFR 46 Subpart B) be enrolled in the research?

No

E4. Neonates

Will neonates of uncertain viability or nonviable neonates (as described in 45 CFR 46 Subpart B) be enrolled in the research?

No

E5. Children

Will children be enrolled in the research?

No

Section F: Design/Procedure

F1. Design

Select one category that most adequately describes your research:

c) Pilot

Discuss the research design including but not limited to such issues as: probability of group assignment, potential for subject to be randomized to placebo group, use of control subjects, etc.

In this proof of concept, intent to treat trial, 30 consecutive patients with diabetes and lower extremity edema will be recruited from the outpatient clinic at Baylor College of Medicine. Patients will be consented per the local Institutional Review Board's guidelines and approval for this study.

Inclusion Criteria:

a) Males or females age 18-90 years old with history of type 1 or 2 diabetes and the ability and willingness to provide Informed consent b) Patients at risk of developing diabetic foot ulcers c) Patient is willing to participate in all procedures and follow up evaluations necessary to complete the study. d) Patients who have undergone lower extremity surgery / amputation may be enrolled into the study at the clinical judgment of the Investigator

Exclusion Criteria:

a) Patients with severe peripheral vascular disease (ABI or ankle brachial systolic pressure index <0.5) b) Patients with diabetic foot ulcers in the plantar foot region c) Patients with active wound infection, or untreated osteomyelitis d) Patients currently on immunosuppressive drugs. e) Pregnant or breastfeeding females. (standard urine pregnancy done on women during physical exam procedures) f) Acute fractures of the foot g) Acute heart failure h) Participation in an interventional Study within the last 30 days i) Non-ambulatory or unable to stand without help or walk a distance of at least 6 feet without assistance. k) Patients with major foot amputation. j) Patients who are unable or unwilling to participate in all procedures and follow up evaluations h) Patients with major foot deformities which won't fit in the diabetic shoes

F2. Procedure

Following is a summary of study procedures:

Study Day 0 (initiation), Visit 1 The following baseline values will be assessed and documented.

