Screening/ Baseline: Subjects will be screened to ensure that they meet the inclusion criteria of the study. The study will be fully explained and written informed consent will be obtained from each patient prior to the initiation of screening procedures.

Cognitive assessment: The Montreal Cognitive Assessment (MOCA) is a series of questions used to assess cognitive status. A score less than 26 could indicate cognitive impairment. Although it is not an exclusion criteria, a score less than 26 will require PCP permission. Written permission from the patient will be asked for in order to contact their PCP for approval to participate in the study.

Physical exam: Physical exam will be conducted, including vascular, dermatological, and neurological, as part of a regular care visit.

Medical History: A detailed medical history will include: previous medical history, location and duration of previous ulcers, amputation (toe, foot, below knee, above knee), lower extremity bypass, lower extremity angioplasty, CABG, cardiac angioplasty, last visit by physician (in weeks), and current/past use of special shoes or insoles.

Neurological Evaluation: The Neurological assessment will consist of Vibratory Perception Threshold testing (VPT) using the technique described by Young [12], and the 10 gram Semmes-Weinstein monofilament using the criteria described by Armstrong and Lavery[13]. The presence of sensory neuropathy will be identified as vibratory perception threshold greater than 25 volts or inability to accurately perceive a 10 gram Semmes-Weinstein monofilament at 1 or more of 10 test sites on the sole and dorsum of the foot[14], which is a standard clinical measurement in diabetic patients.

Vascular Assessment: The vascular assessment will consist of palpation of the dorsalis pedis and posterior tibial arteries and non-invasive Doppler studies. Ankle Brachial Index (ABI) will be determined for both extremities [14, 15]. ABI ratios less than 0.5 will indicate severe vascular disease. These patients will be eliminated from the study per exclusion criteria.

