The researchers will take digital photographs of you and videotape you and your feet during the study to monitor progress or deterioration (worsening) due to intervention. This is done using a normal digital camera for visual images and a thermal (heat sensitive) camera for thermal images. Both these methods are non-invasive. **We will NOT blur your face out in the photographs/videos. While we do all our efforts to mask your face in some cases (for example, journal policy) this may not be practical. We will only use videos and photos of you for scientific presentations or scientific publications. Initial your decision below.

I agree to have my photographs/videotape presented in scientific presentation or scientific publication

I do NOT agree to have my photographs/videotape presented in scientific presentation or scientific publication

Please provide below your Emergency contact information:

Contact name: _____

Relationship: _____

Phone number: _____

Section G: Sample Size/Data Analysis

G1. Sample Size

How many subjects (or specimens, or charts) will be used in this study?

Local: 50 Worldwide: 50

Please indicate why you chose the sample size proposed:

This is an initial proof of concept pilot study. The results of this study will allow for the calculation of an appropriate sample size for a larger proof of superiority (over current standard of care) trial.

G2. Data Analysis

Provide a description of your plan for data analysis. State the types of comparisons you plan (e.g. comparison of means, comparison of proportions, regressions, analysis of variance). Which is the PRIMARY comparison/analysis? How will the analyses proposed relate to the primary purposes of your study?

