Statistical Analysis - This study includes three hypotheses. To examine whether the proposed micro-mobile foot compression device will result in a edema reduction compared to the baseline (H1), we will use ANOVA and Fisher's exact tests for intra-subject rate of edema reduction using the outcome explained before. Multivariate and multiple linear regression test will be used for testing the effects of confounding factors including age, gender, BMI, foot insensitivity, etc. Additional, paired t-test will be used to examine whether amount of edema reduction at the end of study is significant compared to baseline. We will use Pearson correlation of coefficient and Fisher's exact tests to examine whether severity of neuropathy has any significant association with the rate of edema reduction. Finally, we will use multiple linear regression model to examine whether subject's level of activity, BMI, ABI, Skin perfusion pressure, and micro-mobile foot compression device are independent predictors for the rate of edema reduction.

To examine whether the proposed sock will help improve macro and micro-circulation in the lower extremity of patients (H2), we will use the similar analytical plan explained above by considering change in Skin perfusion pressure and ABI as dependent variables. For identifying the predictors, we will use multiple linear regression model and Anova (n-way). The independent variables will be severity of neuropathy quantified using Semmes Weinstein Monofilament, the level of activity, BMI, and age.

To examine whether the proposed socks will improve the activity level and quality of life (H3), we will use ANOVA multivariate test. The dependent variables will be number of total steps per day, duration of walking and standing, duration of longest episode of walking (i.e. continuous walking without stop), number of walking episode, duration of sit-to-stand and stand-to-sit postural transition, and SF12. We will use multiple linear regression model and multi-variant test to examine the effect of confounding parameters such as weather condition, BMI, age, etc.

Section H: Potential Risks/Discomforts

H1. Potential Risks/Discomforts

Describe and assess any potential risks/discomforts; (physical, psychological, social, legal, or other) and assess the likelihood and seriousness of such risks:

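### Section G2 tests the same secondary associations by both a continuous and a categorical method, with no cut-points and no test named as deciding

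*Combined protocol and SAP*

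**What the plan says.** All the analyses at issue are in section G2 (Data Analysis).

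- **H1, neuropathy.** A Pearson correlation and Fisher's exact tests are both planned "to examine whether severity of neuropathy has any significant association with the rate of edema reduction".
- **H2, predictors of change in skin perfusion pressure and ABI.** "For identifying the predictors, we will use multiple linear regression model and Anova (n-way"). The predictors are then listed: "The independent variables will be severity of neuropathy quantified using Semmes Weinstein Monofilament, the level of activity, BMI, and age".
- **Not stated for either pair:** cut-points, number of factor levels, interaction terms, significance level, or which of the two methods decides.

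The monofilament appears in section F2 (Neurological Evaluation). There the presence of neuropathy is defined by a vibration threshold above 25 volts or "inability to accurately perceive a 10 gram Semmes-Weinstein monofilament at 1 or more of 10 test sites". No rule for scoring severity is given.

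The documents state two sample sizes. Section D says "conduct an observational study with N=30 patients", and section F1 says "30 consecutive patients with diabetes and lower extremity edema will be recruited". Section G1 says "Local: 50 Worldwide: 50". G1 gives no power calculation; its reason for the size begins "This is an initial proof of concept pilot study".

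**The concern.** Each pair puts one question to two methods that use the data differently. Pearson correlation and linear regression take the measurements as they are. Fisher's exact test works on a contingency table, so edema reduction must be cut, and severity too unless it is already a category. If the n-way ANOVA takes factors, then activity, BMI and age must be cut. If it takes continuous terms, it is the regression already listed.

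Three things follow. The two tests in a pair will often disagree on significance, and the plan does not say which to believe. Cut-points can be chosen after the data are seen. Reporting whichever test succeeds inflates the false-positive rate. G1 says the results will be used to size a larger trial, so associations reported from this pilot may be carried forward.

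**Working it through.** **Inputs.** From the documents: n = 30 (sections D and F1) or 50 (G1), and four H2 predictors (G2). Assumed, because the documents are silent: two-sided 0.05, bivariate normal data, true correlation r from 0.3 to 0.7, and median splits. The plan states no power figure, so there is none to reproduce.

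**1. Pearson against Fisher's exact test.** Simulation, 20,000 trials per setting. The Pearson test uses t = r√[(n−2)/(1−r²)] on n−2 degrees of freedom. Fisher's test is applied to the 2×2 table of median splits.

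| n | r | Pearson power | Fisher power | Pearson significant, Fisher not |
|---|---|---|---|---|
| 30 | 0.3 | 37% | 12% | 27% |
| 30 | 0.4 | 61% | 21% | 42% |
| 30 | 0.5 | 82–83% | 34% | 49% |
| 30 | 0.6 | 95% | 52% | 44% |
| 30 | 0.7 | >99% | 71% | 28–29% |
| 50 | 0.4 | 84% | 33–34% | 51–52% |
| 50 | 0.5 | 97% | 53–54% | 43–44% |
| 50 | 0.6 | >99% | 75% | 25% |

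Ranges show the spread between repeated runs. As a check, the Fisher-z approximation for Pearson at n = 30, r = 0.5 is Φ(atanh(0.5)·√27 − 1.96) = Φ(0.894) = 81%.

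Part of the gap is discreteness. With 30 patients split 15/15 on both variables, Fisher's p-value is 0.143 when 10 of the 15 high-severity patients are also high on edema reduction, and 0.027 when 11 are. The attained null error is therefore about 2.7%, not 5%.

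**2. Null error if either test counts.** At r = 0, at least one of the two is significant in about 7% of trials at n = 30 and about 6.3% at n = 50. This is before any choice among cut-points.

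**3. Four-factor ANOVA, full factorial.** Two levels per factor give 2⁴ = 16 cells.

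- Patients per cell: 30/16 = 1.9, or 50/16 = 3.1.
- Expected empty cells, if equally likely: 16·(15/16)³⁰ = 2.3, or 16·(15/16)⁵⁰ = 0.6.
- Chance that no cell is empty (inclusion–exclusion): 4.6% at n = 30, 50% at n = 50.

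Three levels give 3⁴ = 81 cells, so at least 81 − 30 = 51 are empty at n = 30. Even stopping at two-way terms needs 1 + 8 + 6·4 = 33 parameters for 30 patients.

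**4. Four-factor ANOVA, main effects only.** This can be fitted. At n = 30 it leaves 30 − 5 = 25 residual degrees of freedom with two levels, or 30 − 9 = 21 with three. Simulation used four independent normal predictors, one active, residual SD 1, n = 30 and 4,000 trials:

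| Slope (SD) | Regression, continuous | ANOVA, median splits | Relative loss |
|---|---|---|---|
| 0.3 | 30% | 20% | 34% |
| 0.5 | 66% | 44% | 34% |
| 0.7 | 90% | 70% | 22% |

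At n = 50 the relative loss runs from 7% to 33%.

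**The case against.** The strongest reply is that the more powerful analyses are already in the plan. A reader might infer that the trial categorizes its predictors and so discards over half its power. The documents do not support that. G2 never says it will categorize; this is implied by Fisher's test and is only the ordinary reading of n-way ANOVA. Pearson correlation and regression stand in the same sentences. A loss above half is also confined to Fisher's test in certain settings. With median splits it is (83 − 34)/83 = 59% at n = 30 and r = 0.5, but 46% at r = 0.6, and 45% at n = 50 with r = 0.5. It does not apply to the main-effects ANOVA.

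A reader might also infer that 30 patients cannot support an n-way ANOVA at all. That is true of a full factorial, which G2 does not specify, and untrue of main effects.

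Nor does F2 reduce the monofilament to a yes/no result. Its rule defines presence of neuropathy; ten sites are tested, so a count from 0 to 10 is available. If severity were nonetheless analysed as present or absent, cut at the median, Pearson would lose power too. At n = 30 and an underlying correlation of 0.5 the comparison would be 61% against 35%.

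Finally, a significant Pearson beside a non-significant Fisher is a difference in sensitivity, not a pair of contradictory findings.

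All of this stands, and it narrows the point. It does not remove it: listing the stronger test beside the weaker one, with neither named as deciding, is what creates the conflict.

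**Conclusion.** The point holds as one of duplicated, under-specified secondary analyses. Under the stated assumptions, the two neuropathy tests differ on significance in over four trials in ten for correlations of 0.4 to 0.6 at 30 patients, and an either-test claim carries about 7% null error. A full four-factor ANOVA would often leave high-order interactions not estimable; a main-effects version repeats the regression with less information. The power figures depend on the assumed significance level, normality, correlations and splits. The absence of cut-points, of a deciding test and of a severity score does not.

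The consequence is modest. These are association and predictor analyses in a pilot, and the paired t-test of edema against baseline is untouched. A reader should not infer that the main edema result is at risk from this point.

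**What to change.** In G2:

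1. **H1, neuropathy association.** Delete Fisher's exact test here and keep the planned correlation as the only deciding analysis, with a 95% confidence interval. For scale, an observed correlation of 0.5 at n = 30 gives tanh(0.549 ± 1.96/√27), about 0.17 to 0.73.
2. **H2 predictors.** Delete the n-way ANOVA. Fit one main-effects linear regression per outcome (change in skin perfusion pressure, change in ABI) with the four predictors entered as continuous variables, and report coefficients with 95% confidence intervals.
3. **Severity.** Define it as the number of insensate monofilament sites, 0 to 10, rather than present/absent. The vibration threshold in volts, already collected, may be named as a supportive measure. The monofilament need not be replaced as the main measure, nor Pearson by a rank correlation.

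The cost is a change of wording. No new data, visits or patients are needed. What is given up is any test of interactions, which a sample of this size could not reliably support.

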Other assessments: Other relevant assessments are Demographic/Health questionnaire, the Mini-Metal State Exam, the mobility-tiredness scale, Barthel Index, Depression Scale, fear of falling (Short-Falls Efficacy Scale – International)[25], quality of life (SF-12 Health Survey)[26], Fried Frailty Criteria, Foot Questionnaire, Pain Assessment, Fall Log and Contact Agreement, Physical activity log, follow-up questionnaire, and Shoe-fit test

AVEX insole: The AVEX insole will be given to the subject. The research personnel will adjust the clutching reel (BOA technology) in order to ensure a comfortable shoe fit. The research personnel will also provide device education to the subject and will answer any questions which may arise.

Study Day 1, Visit 2 48-hour follow up: All participants will be asked to return to clinic approximately 48 hours after visit 1. In this visit, (1) any adverse events will be assessed; (2) activity measurement (body sensor) will be returned; (3) AVEX insole data will be downloaded to ensure operability and patient compliance; and (4) further device education will be provided in case any issues have risen

Study Day 2, Visit 3 1-week follow-up: All participants will be asked to return to clinic approximately 1 week after visit 1. In this visit, (1) any adverse events will be assessed; and (2) AVEX data download to ensure operability and patient compliance. Device education will be provided if needed. The subject will be asked to return the device at their next visit. Similar assessments performed during visit 1 may be performed again during this visit.

Study Day 3, Visit 4 4-week follow-up: All participants will be asked to return to clinic approximately 4 weeks after visit 1. In this visit, outcome assessment using similar assessments described for Study Day 0 will be performed. In addition, benefit and user-friendliness of the AVEX insoles and Boa Technology 'Clutch Reel' will be assessed using a questionnaire. The subject will return the device back to the research personnel.

Patients will be asked to wear a comfortable shirt which holds a small activity monitor (PAMSys) for a period of 48 Hours (2 days). Patients will be requested to return this device via a pre-paid FEDEX envelope

Study Day 4, Visit 5 Three month follow-up: All participants will be contacted by the study coordinator approximately three months post the last study visit (Visit 4) to document potential incident of diabetic foot ulcer or falls.

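### H3 tests SF12 only jointly with the sensor activity outcomes, so quality of life gets no answer of its own, and a complete-case run also drops completed SF12 pairs

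*Combined protocol and SAP*

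**What the plan says.** **The test.** Section G2 covers Hypothesis 3 in one short paragraph: "To examine whether the proposed socks will improve the activity level and quality of life (H3), we will use ANOVA multivariate test". The outcomes follow in a single list. It opens "The dependent variables will be number of total steps per day, duration of walking and standing, duration of longest episode of walking", goes on to the number of walking episodes, and closes "duration of sit-to-stand and stand-to-sit postural transition, and SF12". The only other H3 analysis is for confounders: "We will use multiple linear regression model and multi-variant test to examine the effect of confounding parameters such as weather condition, BMI, age, etc". Its outcome is not named. For H1, by contrast, the same section adds a paired t-test of the change from baseline.

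**How the data arrive.** Section F2 lists SF12 among the other baseline assessments ("quality of life (SF-12 Health Survey") and has assessments similar to those of Day 0 repeated in clinic at Visit 4. The sensor data take a different route. At Visit 2 the baseline recording comes back in clinic: "activity measurement (body sensor) will be returned". The 48-hour recording described directly after Visit 4 does not: "Patients will be requested to return this device via a pre-paid FEDEX envelope". Visit 5 is a contact by the coordinator about three months later and is not described as a clinic visit.

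**What is not stated.** The documents give no rule for missing recordings and no analysis set for H3. Section F1 calls the trial intent to treat without defining the term.

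**The concern.** Aim 3 and Hypothesis 3 name quality of life as something the device should improve. The only test named for it is shared with about seven sensor outcomes, which has two consequences.

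1. **Interpretation.** A significant joint result says that something in the set changed, not that SF12 did. A non-significant one may only mean that a change in SF12 was diluted by sensor outcomes that did not move.
2. **Missing data.** A standard multivariate ANOVA needs a complete outcome vector for each patient. SF12 and the second recording can go missing for different reasons: one is a form completed in clinic, the other a home recording that must be worn, must work and must be posted. Section H1 itself mentions a small risk of sensor malfunction. Under complete-case handling, loss of the recording removes a usable SF12 pair from the only named test of quality of life.

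**Working it through.** The documents give no power, alpha, effect size, standard deviation or return rate, so there is no figure of the plan's to reproduce.

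**Inputs from the documents**
- Sample size: 30 (Sections D and F1) or 50 (Section G1). Both are carried, since the documents do not reconcile them.
- Outcomes in the joint test: steps, walking duration, standing duration, longest walk, number of walking episodes, sit-to-stand duration, stand-to-sit duration, and SF12. That is 7 + 1 = 8, counting SF12 as one score; the plan does not say whether one total or two component scores are used.

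**Assumptions, not in the documents**
- Two-sided 5% level.
- Mean SF12 change of 0.5 SD of the change scores.
- Sensor outcomes unchanged and uncorrelated with SF12 and with each other.
- 0, 10, 20 or 30% of second recordings missing; SF12 complete.

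**Step 1. Does the joint test drop the patient?** The standard routine was run on 30 simulated patients, with SF12 present in all and the sensor outcomes missing in 6. It used 24 rows (F on 8 and 16 degrees of freedom). Six observed SF12 values were left out.

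**Step 2. Power of the joint test.** On change scores this is a one-sample Hotelling T² test. With n complete cases and p = 8, F = T²(n − p) / [p(n − 1)] has p and n − p degrees of freedom and noncentrality n × Δ². Only SF12 moves, so Δ² = 0.5² = 0.25.

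| Planned N | Missing | n kept | df | n × 0.25 | Joint power |
|---|---|---|---|---|---|
| 30 | 0% | 30 | 8, 22 | 7.50 | 32.5% |
| 30 | 10% | 27 | 8, 19 | 6.75 | 28.0% |
| 30 | 20% | 24 | 8, 16 | 6.00 | 23.6% |
| 30 | 30% | 21 | 8, 13 | 5.25 | 19.3% |
| 50 | 0% | 50 | 8, 42 | 12.50 | 61.3% |
| 50 | 10% | 45 | 8, 37 | 11.25 | 54.7% |
| 50 | 20% | 40 | 8, 32 | 10.00 | 47.5% |
| 50 | 30% | 35 | 8, 27 | 8.75 | 40.1% |

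With two SF12 scores (p = 9) and the same Δ², the figures are slightly lower: 29.7% with 30 patients and 57.9% with 50 when nothing is missing.

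**Step 3. Power of SF12 alone.** Paired t-test, noncentrality 0.5 × √N. For N = 30 this is 2.74 on 29 df, power 75.4%. For N = 50 it is 3.54 on 49 df, power 93.4%. Neither depends on the sensor returns.

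**Step 4. Where the loss comes from.** With 30 patients, joint testing alone costs 75.4 − 32.5 = 42.9 percentage points. Missing recordings then cost a further 32.5 − 28.0 = 4.5 points at 10%, 8.9 at 20% and 13.2 at 30%. With 50 patients, joint testing costs 93.4 − 61.3 = 32.1 points, and missing recordings a further 6.6, 13.8 and 21.2. In every row the larger part comes from bundling.

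**Step 5. Cost of adjusting for the extra test.** If H3 is split into two tests at 2.5% each, the paired SF12 test has 64.7% power with 30 patients and 88.5% with 50, still above every joint figure for the same N.

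**The case against.** The strongest reply is that the plan never prescribes a complete-case analysis. It is silent on missing data, and imputation or a likelihood-based repeated-measures model would keep the patient. This stands: the loss follows from the usual form of the named test, not from a written rule.

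The plan's wording is also loose. Analysing each listed outcome in turn is not excluded, and the confounder regression could take SF12 as its outcome. That stands as a possibility, but neither is stated, and one joint test is the natural reading.

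A reader might go further and infer that a patient without the recording cannot be scored for quality of life. The documents do not support that. SF12 is a questionnaire scored without the sensor; only the contribution to the joint test is at risk. A reader might also infer that the reported SF12 change will be biased towards engaged, active patients. Nothing in the documents shows that posting the sensor back tracks SF12 change, and nothing in G2 limits a descriptive SF12 mean to patients with recordings. The undefined reference to intent to treat, in a single-arm study, does not settle the matter.

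The power figures also rest on a case unfavourable to the joint test. If the sensor outcomes changed too, or were correlated with SF12, its power could be higher. A rejection would still not show which outcome had changed.

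Finally, this is a pilot that claims no power, and SF12 is not among the listed primary or secondary endpoints. That limits the weight of the point but does not remove it.

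**Conclusion.** The concern holds in a limited form. H3 names no analysis that answers the quality-of-life question specifically. The main weakness is the bundling of SF12 with the sensor outcomes; loss of completed SF12 pairs is an added risk if the test is run on complete cases.

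The range of joint power, 19.3 to 32.5% with 30 patients and 40.1 to 61.3% with 50, depends wholly on the assumed 0.5 SD change, the 5% level, the unchanged and uncorrelated sensor outcomes and the 0 to 30% loss. The actual return rate is unknown. That a joint test does not isolate SF12 depends on none of these assumptions.

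The point is minor to moderate: it touches a named hypothesis but no listed endpoint.

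**What to change.** In the H3 paragraph of Section G2:

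- Analyse the Visit 1 to Visit 4 change in SF12 on its own, by a paired comparison with a confidence interval, in every patient with both questionnaires. State which SF12 score or scores are used.
- Keep the multivariate test for the sensor activity outcomes, and state how missing recordings are handled.
- Report the number of patients behind each result.

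This takes a few sentences and one extra analysis, with no new data. The cost is one more test within H3: either label it as a separate, unadjusted test or adjust for multiplicity.
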